This is a randomized, double-blind, placebo-controlled parallel design study in which 42 subjects will be randomized (1:1) to treatment with canagliflozin 300mg or placebo once daily for 18 weeks. The study will include 7 outpatient visits which will take place in the Harvard Catalyst Clinical Research Center at BIDMC. The funding source for this study is Janssen Scientific Affairs, LLC; Janssen Scientific Affairs, LLC is also providing canagliflozin for this study.

Our primary endpoint is change in body weight. Secondary endpoints are change in resting metabolic rate measured using indirect calorimetry, change in body composition using DXA scans changes in serum markers of metabolism and inflammation, and change in hunger and satiety using visual analog scales. We will also analyze change in caloric intake using food logs.

Study procedures include a screening visit, an enrollment visit (study week 0), follow-up visits at study weeks 2, 4, 8, and 12, and a final visit at study week 18.

Screening visit: Screening procedures will occur after an overnight fast and will include a full medical history: history of diabetes care and blood sugar control; review of body weight history; review of current medications; a physical exam including height, weight, blood pressure and heart rate; a blood test to measure CBC, electrolytes, kidney function, liver function, thyroid function, cholesterol levels, hemoglobin A1C, and markers of metabolism and inflammation. We will also collect a urine sample for measurement of glucose andcreatinine. We will also measure urine glucose and creatinine levels.

Women of childbearing age will have a urine pregnancy test unless they are over age 50 and have not had a menstrual period in more than 2 years, or have had a surgical procedure which makes it impossible to become pregnant (hysterectomy). If the pregnancy test is positive, the subject will not be allowed to enroll in the study.

Enrollment visit (Study Week 0): The enrollment visit will occur after an overnight fast and will include measurement of vital signs, body composition, and resting metabolic rate. We will also distribute blood sugar logs, visual analog scales, and food logs, and we will do a 24-hour food recall assessment.

Vital signs: For all visits, vital signs will include weight (with the subject wearing a hospital gown), blood pressure lying down and standing, heart rate lying down and standing, and waist circumference.

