Body composition: We will measure body composition using a Dual Energy X-ray Absorptiometry (DXA) scan.

Resting metabolic rate: Resting metabolic rate (RMR) is the number of calories a person's body burns while at rest. Subjects will lay in bed and breathe comfortably without falling asleep for about 20 minutes. After this, we will place a large plastic dome over the subject's head, including the nose and mouth, and we will measure the air the subject inhales and

exhales for about 20 minutes. By measuring oxygen consumption and CO2 production, we can calculate resting metabolic rate.

Blood sugar logs: We will provide blood sugar logs for subjects to record blood sugar levels at least once every day. If subjects already have their own blood sugar logs which they use regularly, they will be allowed to continue to use those during the study.

Visual analog scales: Subjects will be asked to draw a vertical line through a 10cm horizontal line, with one end representing hunger and the other end representing fullness. They will complete these in the fasting state and in the full state (2 hours after a meal) once per week, and at every study visit.

Food recall and food logs: Subjects will be asked to name all of the food eaten in the 24 hours prior to the screening visit so that we can understand baseline eating habits.

Follow-up visits: Study weeks 2, 4, 8, 12

Follow-up visits will occur after an overnight fast and will include

A urine pregnancy test if this was required at the screening visit

A review of adverse effects, changes in medical history, blood sugar logs and compliance with study treatment/placebo

Measurement of vital signs

Collection of a urine sample for measurement of glucose and creatinine.

Measurement of resting metabolic rate

Collection of food logs, blood sugar logs, and visual analog scales

Final study visit (Study week 18)

The final study visit will occur after an overnight fast. Study procedures at this visit are the same as those done at the enrollment visit, above.

Adverse Event Definitions and Classifications

Unlisted (Unexpected) Adverse Event/Reference Safety Information

An adverse event is considered unlisted if the nature or severity is not consistent with the applicable product reference safety information. For canagliflozin the expectedness of an adverse event will be determined by whether or not it is listed in the Investigator's Brochure.

Special Reporting Situations

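### No listed procedure secures a pre-treatment after-meal hunger/fullness rating, so the planned change score and baseline covariate for the fed condition are not assured

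*Combined protocol and SAP*

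**What the plan says.** Section B3.A (Study Design) names "change in hunger and satiety using visual analog scales" among the secondary endpoints. Under Visual analog scales, the instrument is a single 10 cm line running from hunger at one end to fullness at the other. On timing the plan says "They will complete these in the fasting state and in the full state (2 hours after a meal) once per week"; the full frequency instruction is "once per week, and at every study visit".

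The scales first appear at the enrollment visit (study week 0): "We will also distribute blood sugar logs, visual analog scales, and food logs". Of that visit the plan says "The enrollment visit will occur after an overnight fast and will include measurement of vital signs, body composition, and resting metabolic rate". Screening is also held after an overnight fast, and its list of procedures contains no scale. For weeks 2, 4, 8 and 12, "Follow-up visits will occur after an overnight fast and will include" introduces a list that contains "Collection of food logs, blood sugar logs, and visual analog scales". The week-18 visit is again fasting and repeats the enrollment procedures. No visit description mentions a meal, and no run-in is described.

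Section B3.B (Statistical Considerations, Data analysis) applies the ANCOVA of the primary endpoint to the secondary endpoints, with treatment as the fixed effect and each endpoint's own starting value as covariate.

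**The concern.** The endpoint is a change and the model is baseline-adjusted, so each condition in which the scale is completed needs a value from before treatment. Following the schedule as listed, a subject arrives fasting at week 0, receives the scales, and makes the first after-meal rating at home afterwards. By then study treatment may have begun.

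The after-meal rating bears directly on whether the drug alters appetite, in a study of the mechanisms of weight loss. Without a fed baseline, the analyst would have to improvise, and the two obvious substitutes are poor. Subtracting the fasting week-0 rating from a later fed rating would put the ordinary fasting-to-fed shift into the reported change. Adjusting for the first home rating could mean adjusting for an on-treatment value, which would remove part of any early drug effect. The plan proposes neither, but it does not say which rating is the baseline.

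**Working it through.** The plan gives no figure on this point to reproduce. The check compares the schedule with the needs of the analysis, then sizes the loss under stated assumptions.

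**Step 1: which visits could supply a pre-treatment rating.** The seven visits are screening, week 0, and weeks 2, 4, 8, 12 and 18. If dosing starts at or just after week 0, as an 18-week treatment count ending at the week-18 visit suggests, the last five are on treatment. Only screening and week 0 are relevant.

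| Visit | State on arrival | Meal listed | Scales available | Fasting rating | Fed rating |
|---|---|---|---|---|---|
| Screening | Overnight fast | No | Not listed | Not listed | Not listed |
| Week 0 | Overnight fast | No | First distributed | Obtainable | No step described |

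Neither visit has a listed step that yields a rating two hours after a meal. With no run-in and no scales handed out before week 0, home ratings cannot fill the gap before that visit.

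**Step 2: the every-visit instruction.** Read literally, it asks for both conditions at each visit, week 0 included. Every visit follows an overnight fast, and none lists a meal or a two-hour wait. The plan does not say how the fed rating would be obtained.

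**Step 3: what the analysis needs.** The fasting condition can have a week-0 value and so fits the planned ANCOVA. The fed condition has no assured value for the change score or the covariate.

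**Step 4: precision lost without the covariate.** Let r be the correlation between baseline and follow-up fed ratings. The documents give no value, so r is assumed over a range. Compared with an unadjusted comparison of follow-up ratings, and ignoring the one degree of freedom spent, a baseline covariate multiplies the residual variance by 1 − r² and the standard error by √(1 − r²).

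| Assumed r | 1 − r² | √(1 − r²) | Reduction in SE |
|---|---|---|---|
| 0.3 | 0.91 | 0.954 | about 5% |
| 0.5 | 0.75 | 0.866 | about 13% |
| 0.7 | 0.51 | 0.714 | about 29% |

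In terms of sample size, 42 subjects without the covariate carry about the information of 42 × 0.91 = 38, 42 × 0.75 = 32 or 42 × 0.51 = 21 subjects with it.

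**The case against.** A reader might infer that the after-meal rating has no pre-treatment value at all, so that its change cannot be computed. The documents do not support that. The every-visit clause nominally covers week 0. An overnight fast fixes the subject's state on arrival, not for the rest of the visit. The enrollment description is not evidently complete, since it does not mention randomisation or dispensing of study drug either. The time of the first dose is not stated, so an after-meal rating after the week-0 visit but before the first dose is not ruled out. What stands against this is that nothing in the plan requires or arranges such a rating, so whether it exists would depend on how events happened to fall at home.

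A reader might also infer that the satiety half of the endpoint lacks a baseline. That misreads the instrument. Every rating, fasting or fed, places the subject on the same hunger-to-fullness line, so a fasting week-0 rating does give a baseline for the named endpoint in the fasting condition. Only one of two measurement conditions is affected.

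Finally, the trial is randomised and double-blind, so the arms can be compared on post-baseline fed ratings without bias from the missing covariate. This is correct, and it limits the damage. It is not, however, the change endpoint or the baseline-adjusted model that the plan specifies. The gain in precision may also be small: a single home rating after an unstandardised meal could correlate weakly with later ones, which is why the range above starts at r = 0.3.

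**Conclusion.** The point holds as a gap in the schedule for the fed condition. Neither of the two visits that could precede treatment has a step that secures a rating two hours after a meal, and the every-visit instruction does not fit visits held fasting with no meal listed. The fed change score and its planned covariate are therefore not assured, although they are not shown to be unobtainable.

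The cost is moderate. It falls on one condition of one secondary measure and leaves the body-weight endpoint untouched. A valid between-arm comparison of later fed ratings remains. The precision forgone is about 5% to 29% of the standard error for r between 0.3 and 0.7. Two assumptions carry the conclusion: dosing starts at or just after week 0, and r lies in that range. The documents settle neither.

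This is more than a missing detail of wording, because a site that follows the listed schedule would get a worse analysis of the fed condition than the plan intends.

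**What to change.** Distribute the scales at screening. Have each subject complete one fasting and one two-hours-after-meal rating at home before the first dose, and collect both at week 0 as the baseline for the respective condition. In Section B3.B, state that the two conditions are analysed separately, each with its own baseline as covariate. Reconcile the every-visit instruction with the fasting visits, either by limiting the visit rating to the fasting condition or by describing how a fed rating is obtained once the fasting procedures are finished. State when the first dose falls relative to the week-0 visit, so that it is clear which ratings precede treatment.

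The cost is two short extra home ratings per subject, scales handed out one visit earlier, and a few lines of protocol text. No extra visit is needed. The change has to be made before subjects start treatment, because a missing baseline cannot be recovered afterwards.

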Major Hemorrhage

Major hemorrhage is defined as any hemorrhagic event that is Grade 3 or greater in severity or that results in 1 of the following: intraocular bleeding causing loss of vision, the need for a transfusion of 2 or more units of red cells or an equivalent amount of whole blood, hospitalization, or prolongation of hospitalization.

Intracranial Hemorrhage

Any intracranial hemorrhage adverse event, including subdural hematoma/hemorrhage, epidural hematoma/hemorrhage and intracerebral hemorrhage, of any grade severity, will be captured as an event of special interest.

Other Malignancies

In addition to all routine AE reporting, all new malignant tumors, including solid tumors, skin malignancies and hematologic malignancies, are to be reported for the duration of study treatment and during any protocol-specified follow-up periods including post-progression follow-up for overall survival.

Pregnancy

All initial reports of pregnancy will be reported to Janssen Scientific Affairs, LLC by study-site personnel within 24 hours of knowledge of the event. Abnormal pregnancy outcomes (eg, spontaneous abortion, stillbirth, and congenital anomaly) are considered serious adverse

events and will be reported as a Serious Adverse Event. Any subject who becomes pregnant during the study will discontinue further study treatment.

Because the effect of the study drug on sperm is unknown, pregnancies in partners of male subjects included in the study will be reported by the study-site personnel within 24 hours of their knowledge of the event.

Follow-up information regarding the outcome of the pregnancy and any postnatal sequelae in the infant will be required.

PRODUCT QUALITY COMPLAINT HANDLING

A product quality complaint (PQC) is defined as any suspicion of a product defect related to manufacturing, labeling, or packaging, ie, any dissatisfaction relative to the identity, quality, durability, or reliability of a product, including its labeling or package integrity. A PQC may have an impact on the safety and efficacy of the product. Timely, accurate, and complete reporting and analysis of PQC information from studies are crucial for the protection of subjects, investigators, and the sponsor, and are mandated by regulatory agencies worldwide.

Procedures

All initial PQCs must be reported to Janssen Scientific Affairs, LLC by the study-site personnel within 24 hours after being made aware of the event.

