If the defect is combined with a serious adverse event, the study-site personnel must report the PQC to Janssen Scientific Affairs, LLC according to the serious adverse event reporting timelines. A sample of the suspected product should be maintained for further investigation if requested by Janssen Scientific Affairs, LLC.

B. Statistical Considerations

Sample Size Justification: There are no published data on change in resting metabolic rate with canagliflozin treatment. We therefore calculated sample size based on change in body weight, our primary outcome. Published data show approximately 3kg placebo-corrected weight loss after 12 weeks of treatment with canagliflozin compared to placebo in individuals with type 2 diabetes and obesity (Stenlof et al, 2013). Based on a 3 kg difference in body weight between canagliflozin and placebo and a SD of 3.3, the probability that this study will detect a treatment difference at a two-sided 0.05 significance level is 80% if we have 42 study completers. We plan to screen 60 subjects in order to enroll approximately 50 subjects (8-10 screen failures) and obtain 42 study completers (approximately 8-10 dropouts). Data from subjects who complete at least 12 weeks of treatment will be used in the final analysis.

Data analysis: Descriptive statistics with 95% confidence intervals will be used to describe baseline characteristics of the study population. The primary endpoints of change in body weight and BMI will be analyzed using an analysis of covariance (ANCOVA) model. We will use repeated measures analysis of variance to assess changes in body weight and resting metabolic rate at each study visit/timepoint. We will also analyze change in body composition between baseline and end of study. Treatment group will be the fixed effect and corresponding baseline values at the start of each treatment period will be the covariates. We will stratify based on baseline BMI, glycemic control (A1C), and diabetes treatment (lifestyle vs pharmacologic treatment at baseline). The least squares mean differences between treatments (canagliflozin vs placebo) and the associated 95% confidence intervals will be estimated based on this model.

Secondary endpoints will be analyzed using an ANCOVA model as above. The least squares mean differences between treatments and the associated 95% confidence intervals will be estimated based on this model.

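### No pregnancy test is listed at either DXA visit (weeks 0 and 18); adding one is a small, cheap safety improvement

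*Combined protocol and SAP*

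**What the plan says.** All the visit procedures are in section B3.A.

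- **Screening:** women of childbearing age have a urine pregnancy test, with exemptions for women over 50 with no period for more than 2 years and for those surgically unable to conceive. The consequence is stated: "If the pregnancy test is positive, the subject will not be allowed to enroll in the study".
- **Week 0:** "The enrollment visit will occur after an overnight fast and will include measurement of vital signs, body composition, and resting metabolic rate". The list goes on to logs, scales and a food recall. Body composition is defined as a DXA scan. No pregnancy test appears.
- **Weeks 2, 4, 8 and 12:** the list begins with "A urine pregnancy test if this was required at the screening visit". No DXA is listed.
- **Week 18:** "Study procedures at this visit are the same as those done at the enrollment visit, above". This brings in the DXA, again without a test.

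Section B5 gives fetal and infant radiation as a reason for excluding pregnant and lactating women. It also requires a negative test before study drug is started, without a time window. Contraception by a method the study doctor has approved before entry and immediate reporting of a suspected pregnancy are required too. The Pregnancy paragraph of B3.A adds: "All initial reports of pregnancy will be reported to Janssen Scientific Affairs, LLC by study-site personnel within 24 hours of knowledge of the event" and "Follow-up information regarding the outcome of the pregnancy and any postnatal sequelae in the infant will be required".

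**The concern.** The four follow-up visits, which involve no radiation, each list a test. The two visits with radiation list none. That sits badly with a protocol that names radiation as a reason to keep pregnant women out.

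At week 0, no maximum interval between screening and enrollment is given anywhere, so the result behind the first scan can be of any age. The same is true of the first dose if it is given at week 0. That timing is inferred and not stated: the overview says that "42 subjects will be randomized (1:1) to treatment with canagliflozin 300mg or placebo once daily for 18 weeks", and the final visit is at week 18.

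At week 18, a pregnancy that began after the week-12 test has no scheduled means of detection before the second scan. This is also the last listed visit. If the pregnancy is missed there, the 24-hour report and the outcome follow-up depend on the participant coming forward. A week-18 test would not prevent or shorten drug exposure already received. Its value is in avoiding one scan and in triggering that follow-up.

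**Working it through.** **1. Tests set against scans (B3.A)**

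| Visit | Urine pregnancy test listed | DXA |
|---|---|---|
| Screening | Yes | No |
| Week 0 | No | Yes |
| Weeks 2, 4, 8, 12 | Yes | No |
| Week 18 | No | Yes (by cross-reference) |

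Tests listed at DXA visits: 0 of 2.

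**2. Age of the latest listed result at each scan**

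- Week 0: equal to the screening-to-enrollment interval, which is not stated.
- Week 18: 18 − 12 = 6 weeks. This uses nominal visit weeks, because no visit windows are given.

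The intervals between successive visits from week 0 are 2, 2, 4, 4 and 6 weeks. The last is the longest and is 6/4 = 1.5 times the next longest. This describes spacing; it is not a measure of risk.

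**3. Radiation (B5, DXA risks)**

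Inputs: 0.04 mSv in total; background 3 mSv per year. The protocol describes the dose as roughly one week of background.

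- Share of a year's background: 0.04/3 = 1.3%.
- In days: 0.04/3 × 365 = 4.9 days, or 0.70 of a week, broadly in line with the protocol's description.
- Per scan, assuming two equal scans: 0.02/3 × 365 = 2.4 days.

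**4. Ceiling on added tests (B3.B, Sample Size Justification)**

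The plan says: "We plan to screen 60 subjects in order to enroll approximately 50 subjects (8-10 screen failures) and obtain 42 study completers". The number of women who need testing is not given. If every enrolled subject needed a test at both visits:

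- with the planned dropout: 50 + 42 = 92 tests;
- with no dropout: 2 × 50 = 100 tests.

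The true number will be lower, since men and exempt women need none.

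**5. Effect of the change**

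The age of the result at the scan falls to 0 weeks at both visits, from unspecified (week 0) and 6 weeks (week 18).

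**The case against.** The strongest reply is that the week-0 and week-18 lists are shorthand. Read literally, week 0 has no randomization and no dispensing. Week 18 has no blood draw, although serum markers are a secondary endpoint, and no adverse-event review. A missing pregnancy test in such a list is weak evidence of a decision not to test, and a site might test anyway. The consent pages, which might mention testing, were not available for this review. This point stands in part: it limits what can be said about actual practice. But the test is named for the follow-up visits and not for week 0, so a site working from the text would scan without a current result.

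Second, no rule is breached. B5 sets no same-day test and no maximum test age, and a test precedes each scan. That is correct, which is why this is a suggestion about design and not an error.

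Third, the risk is already low. The dose is very small, contraception and self-reporting are required, a further test follows at week 2, and B5 states that completed animal studies do not point to birth defects. All of this limits the size of the concern. It does not remove it, because the same contraception and reporting duties apply at weeks 2, 4, 8 and 12 and the protocol tests there anyway.

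Fourth, a test placed before DXA and drug but after randomization would turn a positive result into a post-randomization exclusion. The timing of randomization is not stated. This is a fair refinement and is taken up in the fix.

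**Conclusion.** The concern holds as a minor, optional improvement to participant safety. Neither DXA visit lists a pregnancy test. The result behind the first scan has no set age, and the one behind the second is nominally 6 weeks old. Exposure at stake is 0.04 mSv over the whole study. The benefit is a current result before the first scan and, if dosing starts at week 0, before first drug exposure. At week 18 the benefit is a scan avoided and a late pregnancy identified for reporting and follow-up. Sample size, power and the primary analysis are not affected.

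The conclusion rests on the visit lists as written, on nominal visit weeks and, for the first-dose point only, on dosing starting at week 0.

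**What to change.** Add the line already used for the follow-up visits, "A urine pregnancy test if this was required at the screening visit", to the enrollment visit (Study Week 0) list in B3.A. State that it is done before randomization, before the DXA and before study drug is started. Week 18 then inherits the test through the existing cross-reference; state that there it is done before the second DXA.

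The cost is one line of text plus the week-18 timing note, and at most two extra urine tests per eligible woman, at visits that already exist. A urine sample would be needed at weeks 0 and 18, where none is listed now. The downside is that a positive result means non-enrolment at week 0 or a missing DXA value at week 18.
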